11.4.1.6.1. Relationship to the Investigational product

The causality between each adverse event and the investigational product should be classified according to the following terms:

Tiziana Life Sciences, PLC - Confidential Page 69 of 101

Milciclib maleate (PHA-848125AC)	CDKO-125a-006-P4
Protocol for Study CDKO-125a-006	09 March 2017

Unrelated: the event is a pre-dose event or is definitely due to causes separate from the administration of the investigational product, i.e.: documented pre-existing condition, concomitant medication, the subject's clinical state or the event is judged as not related and does not fall under any of the above points.

Unlikely: an event for which the exclusion of drug causality seems most plausible, whilst other drugs or underlying disease provide plausible explanation.

Possible: a clinical event, including laboratory test abnormality, with a reasonable temporal sequence from administration of the investigational product and with a known response pattern to the investigational product, but the event could have been caused by subject's clinical state, other therapy administered or diagnostic/interventional procedure. Information on drug withdrawal may be lacking or unclear.

Probable: a clinical event, including laboratory test abnormality, with a reasonable temporal sequence from administration of the investigational product and with a known response pattern to the investigational product, but the event cannot be reasonably explained by the known characteristics of the subject's clinical state, other therapy administered or diagnostic/interventional procedure and for which there is evidence of partial or complete disappearance of the event after withdrawal of the product (positive dechallenge).

Definite: a clinical event that follows a reasonable temporal sequence from administration of the drug or in which the drug level has been established in body fluids or tissues; that follows a known response pattern to the suspected drug; and that is confirmed by improvement on withdrawal (positive dechallenge) or reducing the dose, and reappearance of the event after reintroduction of the drug (positive rechallenge).

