9.4.3. Dose Modifications

Dose modifications may occur as a consequence of drug-related toxicities, during a cycle or at the start of a new cycle. In the event of multiple toxicities, dose modifications should be applied based upon the most severe toxicity observed and attributable to PHA-848125AC.

As far as dose reductions are concerned, a dose reduction to the dose level of 100 mg/day (i.e. -33%) is recommended in case of poor tolerability of the full dose of 150 mg/day.

The dose of 100 mg/day (mean Day 7 AUC 19.9 μ M·h) was successfully used for 20 cycles in keeping disease control in a patient with colorectal cancer, initially treated at 150 mg/day for 7 cycles in the CDKO-125a-001 study.

Doses reduced for drug-related toxicity should not be re-escalated. Any exception is to be discussed between the Investigator and the Sponsor.

Table 4 describes the recommended dose modifications during the treatment cycles and at the start of any new cycle.

Note: the dose adjustments in the third column are intended as referred to the dose of Day 1 of the previous cycle.

Toxicity (Graded as per NCI CTCAE Criteria, Version 3.0)	During Treatment Cycle	Dose Adjustment for Next Treatment Cycle (after recovery from toxicities to grade ≤1, or to baseline values) ¶	
Hematologic			
Grade 0 or Grade 1	Maintain dose level	Maintain dose level	
Grade 2 Neutropenia (ANC < 1500-1000/mm ³) and/or Grade 2 Thrombocytopenia (platelet	If occurs during treatment, maintain daily dose level	Maintain dose level	
count <75000-50000/mm3)	Monitor until resolved to grade ≤ 1		
Grade 3 Neutropenia (ANC <1000-500/mm ³)	If occurs during treatment, decrease daily dose by one dose level Monitor until resolved to grade ≤1	Maintain dose level	
Grade 3 Thrombocytopenia (platelet count <50000-25000/mm3), uncomplicated or lasting less than 5 days	If occurs during treatment, decrease daily dose by one dose level Monitor until resolved to grade ≤1	Maintain dose level	
Grade 4 Neutropenia (ANC < 1000/mm³) lasting < 7 days	If occurs during treatment, decrease the daily dose by one dose level Monitor until resolved to grade ≤1	Maintain dose level	
Grade 4 Neutropenia (ANC < 1000/mm ³) lasting 7 days or more			
Febrile neutropenia (ANC <1,000/mm3 and fever of unknown origin ≥38.5°C)			

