9.4.9. Assessment of Potential, Thrombotic Microangiopathy/Hemolytic Uremic Syndrome

Two patients, both treated in the CDKO-125a-004 combination study with gemcitabine ('A Phase I Dose-Escalation Study of Oral PHA-848125AC Administered in Combination with Gemcitabine in Adult Patients with Advanced/Metastatic Solid Tumors'), developed Thrombotic Microangiopathy/Hemolytic Uremic Syndrome (TMA/HUS). The two cases were considered to be probably related to gemcitabine and unlikely related to PHA-848125AC by the participating Investigator, and occurred in patients with very prolonged and high exposure to both drugs (after 14 and 21 months on treatment, respectively); both patients recovered in the opinion of the Investigator, and only one of them required plasmapheresis. No other cases of TMA/HUS were reported in any of the other studies completed or ongoing with PHA-848125AC (all single agent studies). Anyway, taking into consideration the small number of patients treated so far at this stage of development of PHA-848125AC (about 200 patients), a contribution of the study drug on

Tiziana Life Sciences, PLC - Confidential Page 54 of 101 the two observed TMA/HUS events cannot be completely ruled out. As a consequence, special attention should be paid to the following events:

- Progressive increase of anemia up to CTC Grade \geq 3 no otherwise explained
- Progressive platelets decrease up to CTC Grade ≥ 2
- Increase of creatinine (shift to CTC Grade 2) or calculated creatinine clearance diminished by ≥ 25% vs baseline
- Presence of hematuria or proteinuria
- Appearance of high blood pressure in a patient with unknown history or with high blood pressure previously well controlled with medications
- Appearance of oedema concomitant to proteinuria

Whenever ≥ 2 of the above listed alterations appear concomitantly for the first time, or at any time if the Investigator judges it appropriate, study drug administration is to be temporarily held, until further evaluations are done. The latter ones consisting of the search of schistocytes in the peripheral blood smear, the count of reticulocytes in the peripheral blood, coagulation test, total LDH and 24-hour proteinuria [39]. Routine Hematology, Blood Chemistry and Urinalysis tests foreseen by study protocol, should also be repeated at the time when this evaluation is performed.

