12.3.6. Safety Analyses

Safety data will be evaluated in the treated patient population and, if clinically interesting, in other patient subsets (e.g. evaluable patients).

The adverse events (AEs) will be coded by the Medical Dictionary for Regulatory Activities (MedDRA) and their severity graded according to the NCI Common Terminology Criteria for Adverse Events (CTCAE) version 3.0. The MedDRA preferred term and system organ class (SOC) will be used to identify and group events in data listings and descriptive analyses. All reported baseline signs and symptoms and on-treatment adverse events will be reported in the patients' data listings. The analysis will address all the events that are recorded on treatment (i.e. from cycle 1, on). The raw incidence of each sign/symptom, of the subsets of events grouped by system organ class and, in general, the raw incidence of any AE, will be calculated. In this analysis, every patient will be accounted for on the basis of the worst CTCAE grade reported during the whole period, within the considered category (*e.g.* the analyzed sign/symptom or system organ class). The following subsets of AEs will also be specifically considered: serious AEs, AEs with CTCAE grade 3-5, AEs with a relationship to study treatment classified by the Investigator as possible or probable or definite and AEs reported as leading to discontinuation from treatment.

Raw incidence of death will be calculated. Deaths will also be described in terms of relationship to the study treatment and according to the time from treatment stop.

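### As written, a suspected drug reaction of a type not yet described fits none of the five causality classes, so it has no proper route into the related-AE results

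*Protocol*

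**What the plan says.** Protocol section 11.4.1.6.1 gives five causality classes. Possible and Probable share one opening condition, an event "with a reasonable temporal sequence from administration of the investigational product and with a known response pattern to the investigational product".

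- **Possible:** plausible timing and "with a known response pattern to the investigational product, but the event could have been caused by subject's clinical state", other therapy or a procedure.
- **Probable:** plausible timing and "with a known response pattern to the investigational product, but the event cannot be reasonably explained" by other causes, with improvement after withdrawal.
- **Definite:** plausible timing or a measured drug level, an event "that follows a known response pattern to the suspected drug", and both positive dechallenge and positive rechallenge.
- **Unlikely:** "an event for which the exclusion of drug causality seems most plausible, whilst other drugs or underlying disease provide plausible explanation".
- **Unrelated:** an event before dosing, one definitely due to a separate cause, or one judged not related.

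No class has an exception for a new or unexpected type of event.

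Section 12.3.6 uses the classes to form one of its AE subsets: "AEs with a relationship to study treatment classified by the Investigator as possible or probable or definite". It also describes deaths by their relationship to treatment. The same section tabulates all AEs, serious AEs, grade 3-5 AEs and AEs leading to discontinuation without regard to causality.

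**The concern.** The three related classes share one necessary condition: the event must already belong to the drug's known pattern. That is circular. A reaction can be called related only if it is already accepted as something the drug does, while a phase II trial is partly meant to find reactions that nobody has yet described.

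The protocol itself says in section 9.4.9 that experience with the compound is limited, "taking into consideration the small number of patients treated so far at this stage of development of PHA-848125AC (about 200 patients"). The trial has a single arm (section 5) and no data monitoring committee (section 12.5). Without a control group, an all-causality table in advanced cancer does not separate drug effects from disease effects, so investigator attribution carries much of that work. If the scale gives no place to a suspected new reaction, the related-AE results lean towards what is already known. Sites that follow the text and sites that ignore it may also rate the same event differently.

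**Working it through.** The protocol states no figure on this point, so the check is first textual and then illustrative.

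**Step 1: test one event against each class.** Take an event with plausible timing, no other explanation and improvement on withdrawal, of a type not described for this drug.

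| Class | Condition that decides it | Met? |
|---|---|---|
| Possible | known pattern required | no |
| Probable | known pattern required | no |
| Definite | known pattern required (and rechallenge) | no |
| Unlikely | drug cause most plausibly excluded, other explanation available | no |
| Unrelated | pre-dose, definite other cause, or judged not related | no, because the investigator suspects the drug |

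The event meets none of the five definitions. The investigator must pick a class that misdescribes it.

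**Step 2: trace the classes to the outputs.**

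- *Depend on the classification:* the related-AE subset and the description of deaths by relationship (12.3.6). One follow-up rule in 11.4.1.3 also names the classes: unresolved non-serious events are followed if rated Unlikely or higher, so only those rated Unrelated are left out.
- *Do not depend on it:* reporting of all AEs (11.4.1.3), notification of SAEs within 24 hours (11.4.1.4), and the all-AE, serious, grade 3-5 and discontinuation tables and the individual listings (12.3.6).

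**Step 3: how often could it arise?** Inputs: about 200 patients treated so far (9.4.9) and up to 60 enrolled here (12.1). Assumptions: *known* means already seen in those 200; the 60 are separate from the 200; patients are independent; the true frequency p is 1% or 0.5%. The protocol gives none of these four.

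The gap matters only if the reaction is unseen before **and** occurs in the trial:

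P = (1 − p)^200 × [1 − (1 − p)^60]

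- p = 1%: 0.99^200 = 0.134; 1 − 0.99^60 = 0.453; product = 0.061, about 6%.
- p = 0.5%: 0.995^200 = 0.367; 1 − 0.995^60 = 0.260; product = 0.095, about 10%.

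The choice of p does not hide a larger value. Write x = (1 − p)^60, so that P = x^(10/3) × (1 − x). This is greatest at x = (10/3)/(13/3) = 10/13 = 0.769, where P = 0.417 × 0.231 = 0.096. Under these assumptions, about 10% is the ceiling for any single type of reaction.

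**The case against.** The strongest reply is that this is a gap in wording with few consequences. Much of that stands.

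- **Forced rating.** A reader might infer that a new toxicity can only be rated Unlikely or Unrelated. The text does not say so: the event contradicts those two definitions as well. An investigator might choose Probable, which fails on one element, before Unlikely, which contradicts the causal suspicion. So the text does not establish that no such event would ever reach the related-AE table. It gives no proper way in.
- **Disappearance from the safety results.** A reader might infer this too. It is not so: the outputs and reporting routes in the second list of step 2 are untouched, and the secondary safety endpoint in 4.2.2 refers to adverse events emerging in the trial, not to related ones.
- **Dose changes and late reports.** Section 9.4.3 says "Dose modifications may occur as a consequence of drug-related toxicities, during a cycle or at the start of a new cycle", and 11.4.1.3 asks for late serious reactions that the investigator believes related. Neither refers to the five-class scale, so the documents do not show that these rules fail.
- **The TMA/HUS cases in 9.4.9.** They were rated unlikely related to this drug although a contribution could not be excluded, which makes them a tempting example. They came from a combination study whose causality definitions are not shown, and gemcitabine was the probable cause. The sponsor still added precautions triggered by findings, without a causality test. They do not show that this wording suppressed a signal.
- **Meaning of *known*.** The protocol does not define it. If it includes the animal findings in 3.2.5 (CNS, ocular, renal and others), fewer reactions are new and the gap is smaller.

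The reply does not remove the shared condition in the three related classes. Investigators may disregard it in practice, but nothing in the protocol allows them to.

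**Conclusion.** The defect holds in a limited form. All three related classes require a known response pattern, the other two do not fit a suspected reaction, and an event of a new type is left without a class. Followed as written, the rule keeps that event out of the related-AE subset and prevents it from being called related in the summary of deaths. The bias is towards a more favourable related-AE profile.

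The chance that this affects a given type of reaction is about 6% at a true frequency of 1% and about 10% at 0.5%, on the assumptions in the working. These values are illustrative. The separate chances of at least one case among 60 patients, 45% and 26%, should not be read as the size of the problem, because they leave out the condition that the reaction was not seen before.

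The primary endpoint, the two-stage decision rules and SAE reporting are unaffected. The severity is moderate: worth correcting, but not a condition for the trial's validity.

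**What to change.** In section 11.4.1.6.1, in both Possible and Probable, replace the phrase that makes the known pattern an added requirement by: *whether or not the event follows a known response pattern to the investigational product*. Keep the requirement in Definite. Leave the 12.3.6 subset as it is; a first-seen event with plausible timing, no other explanation and positive dechallenge can then be Probable and is counted.

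This protocol version is dated 09 March 2017 and CRF collection of AEs stops at the 31 May 2017 cut-off, so many events will already carry a rating under the present definitions. For these, produce a listing of events rated Unlikely or Unrelated that had a plausible temporal relation to dosing, so that they can be reviewed, and state in the report which definitions applied when.

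The cost is two phrases in the protocol, the matching guidance on the SAE form, one listing with its review, and possibly a slightly less favourable related-AE rate. No endpoint, sample size or treatment rule changes.

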11.4.1.7. Exposure In Utero

The Investigator will be asked to submit an Exposure in Utero Form in the cases reported below:

- a trial patient becomes or is found to be pregnant while receiving an investigational medication/product or within **90 days** of its discontinuation
- a partner of a male patient becomes or is found to be pregnant, while the patient is receiving an investigational medication/product or within **90 days** of discontinuing the investigational medication/product.

This must be done irrespective of whether an adverse event has occurred and within 24 hours of awareness of the pregnancy. The information submitted should include the estimated date of delivery (see below for information related to induced termination of pregnancy). However if the patient begins a new anticancer therapy before **90 days** after the last dose of study treatment administration, the exposure *in utero* reporting period will end at the time the new treatment is started.

Tiziana Life Sciences, PLC - Confidential Page 70 of 101

Milciclib maleate (PHA-848125AC)	CDKO-125a-006-P4
Protocol for Study CDKO-125a-006	09 March 2017

The Investigator will follow the patient until completion of the pregnancy or until pregnancy termination (i.e., induced abortion) and then notify the CLIOSS Pharmacovigilance of the outcome within 5 days or as specified below. The Investigator will provide this information as a follow up to the initial Exposure in Utero form. The reason(s) for an induced abortion must be specified.

If the outcome of the pregnancy meets the criteria for immediate classification as a serious adverse event (i.e., spontaneous abortion, stillbirth, neonatal death, or congenital anomaly [including that in an aborted fetus]), the Investigator should follow the procedures for reporting serious adverse events, i.e., report the event to Nerviano Medical Sciences (as described in Section 11.4.1.4, Reporting Requirements).

In the case of a live birth, the "normality" of the newborn can be assessed at the time of birth (i.e., no minimum follow-up period of a presumably normal infant must pass before an Exposure in Utero Form can be completed). The "normality" of an aborted fetus can be assessed by gross visual inspection unless pre-abortion laboratory findings are suggestive of a congenital anomaly.

Additional information about pregnancy outcomes that are classified as serious adverse events follows:

- "Spontaneous abortion" includes miscarriage and missed abortion.
- All neonatal deaths that occur within 1 month of birth should be reported, without regard to causality, as serious adverse events. In addition, any infant death after 1 month that the investigator assesses as possibly related to the in utero exposure to the investigational medication should also be reported.

11.4.2. Laboratory Safety Assessments

Laboratory safety assessments will include repeated evaluation of hematology and biochemistry parameters, urinalyses and pregnancy test that after the cut-off date of 31 May 2017 will be done according to routine clinical practice and/or at investigator's discretion. The results of these exams should be recorded only in the patient's medical notes..

Hematology tests include: hemoglobin, erythrocytes (RBC), white blood cell (WBC) with differential count (neutrophils, lymphocytes, monocytes, eosinophils, basophils, differential other cells), platelets (PLTs).

They will be performed during screening period and repeated during treatment between the Days 11 and 14 of all cycles. If toxicity preventing re-treatment results from the Day 11-14 assessment, hematology should be repeated as needed to monitor for recovery.

Hematology tests will be done also on Day 1 of cycles, before study drug administration, only in case toxicity preventing re-treatment resulted from the assessment done within the previous 4 days at the end of the prior cycle.

For patients remaining on treatment for a period of time more than 6 cycles and come back

Tiziana Life Sciences, PLC - Confidential Page 71 of 101

Milciclib maleate (PHA-848125AC)	CDKO-125a-006-P4
Protocol for Study CDKO-125a-006	09 March 2017

to the site every 3 cycles, the hematological tests may be done locally when the visit to the site is not planned (one visit planned to the site every three cycles, 1.5 months) and must be sent to the site for safety evaluation and reported on CRF.

Blood chemistry tests include: sodium, potassium, chloride, magnesium, blood urea nitrogen (BUN) or urea, creatinine, albumin, AST/SGOT, ALT/SGPT, Alkaline Phosphatase (ALP), total bilirubin, creatinine clearance (calculated by the Cockroft and Gault's formula), amylase and lipase.

They will be performed during screening period and repeated during treatment between the Days 11 and 14 of all cycles. If toxicity preventing re-treatment results from the Day 11-14 assessment, blood chemistry should be repeated as needed to monitor for recovery. Blood chemistry tests will be done also on Day 1 of cycles, before study drug administration, only in case toxicity preventing re-treatment resulted from the assessment done within the previous 4 days at the end of the prior cycle. For patients remaining on treatment for a period of time more than 6 cycles and come back to the site every 3 cycles, the biochemical tests may be done locally when the visit to the site is not planned (one visit planned to the site every three cycles, 1.5 months) and must be sent to the site for safety evaluation and reported on CRF.

Coagulation tests include: INR (International Normalized Ratio) and activated partial thromboplastin time (APTT, in seconds). To be done at baseline, at the end of last cycle and, during treatment, at the end of even cycles (between Days 11 and 14). For patients remaining on treatment for a period of time more than 6 cycles and come back to the site every 3 cycles, the coagulation tests may be done locally when the visit to the site is not planned (one visit planned to the site every three cycles, 1.5 months) and must be sent to the site for safety evaluation and reported on CRF.

Urinalysis includes: pH, dipstick for glucose, protein and blood. It will be performed at baseline and at the end of last cycle. During treatment, should be performed at the end of even cycles (between Days 11 and 14). For patients remaining on treatment for a period of time more than 6 cycles and come back to the site very 3 cycles, the urinalysis tests may be done locally when the visit to the site is not planned (one visit planned to the site every three cycles, 1.5 months) and must be sent to the site for safety evaluation and reported on CRF.

Serum/urine pregnancy test is indicated only for women of reproductive potential and is to be carried out within 7 days prior to the first treatment administration.

The timing and specific requirements for each laboratory safety evaluation are given in Section 7, Schedule of Events.

Specific analyses to be performed in presence of events indicative of, or suggestive of, MTA/HUS (see Section 9.4.9): search of schistocytes in the peripheral blood smear, count of reticulocytes in the peripheral blood, coagulation test, total LDH and 24-hour proteinuria.

Tiziana Life Sciences, PLC - Confidential Page 72 of 101
Milciclib maleate (PHA-848125AC)	CDKO-125a-006-P4
Protocol for Study CDKO-125a-006	09 March 2017

Routine Hematology, Blood Chemistry and Urinalysis tests, foreseen by the study protocol, should also be repeated at the time when this evaluation is performed.

